12.0 CRITERIA FOR THERAPEUTIC RESPONSE/OUTCOME ASSESSMENT

Primary objectives:

- To evaluate the feasibility of Calypso transponders as an internal tumor surrogate to guide DIBH radiation treatments in real time.
- Feasibility is defined as completion of all treatments using the DIBH treatment plan and Calypso transponders. Patients who cannot have their transponders placed accurately bronchoscopically or for whom Calypso-guided DIBH will not be possible will be considered a failure. Patients who are removed from the protocol as a result of being unable to perform the breath hold for 3 consecutive treatment days at any point in the treatment course for reasons that are not related to the Calypso transponders, Calypso detection or complications of using the Calypso implantation or system (e.g. disease progression, severe side effects from treatment, e.g. esophagitis, infections, failure to thrive, generalized weakness, low blood counts etc.), will be replaced by new evaluable patients. Those patients will be treated with the free-breathing backup radiation treatment plan. The reason for the patient's inability to hold their breath will be recorded.

Secondary objectives:

- To compare the reproducibility with visual versus without visual biofeedback.
- To assess differences in the ability of maintaining the DIBH maneuver within the fate with and without visual biofeedback
- To measure the residual intrafraction tumor motion and associated improvement in normal tissue dosimetry during DIBH based on the Calypso lung transponder signal as a surrogate

- To measure the increase in dose escalation and the potential for decreasing margins made possible by Calypso-guided DIBH
- To determine the minimum clinically feasible gate margin for radiation
- To assess tumor shrinkage, beacon position and centroid changes in conventionally fractionated patients
- To assess intra- and inter-fraction variation in lung volume preservation of multiple DIBH maneuvers

Reproducibility of using internal tumor surrogates (Calypso beacons) during repeated deep inspiration breath hold maneuvers with and without visual biofeedback will be evaluated by posthoc analysis of the Calypso signal traces. The ability to maintain the breathhold to within the tolerance level to which they have been assigned will be assessed. Number of beam holds and treatment interruptions will be recorded as an objective measure of the patient's ability to maintain their breathhold. Whether or not visual biofeedback will aid in the ability to hold their breath reliably and within the target region will be assessed using the number of treatment interruptions. We will also assess differences in duty cycle and number of DIBH attempts with and without visual biofeedback. Differences in the ability of maintaining the DIBH maneuver within the gate with and without visual biofeedback will be measured as duty cycle, a quantifiable measure of how long it takes to deliver a radiation treatment. It is related to how well patients can hold their breath and the tumor in the target position. Each patient will have the goggles 50% of the treatments and without goggles the other 50% of the time. Wilcoxon rank sum tests will be done to compare the duty cycle.

The residual intrafraction motion and drift during DIBH will be determined based on the Calypso signal traces which may provide critical insight into the ability to immobilize the tumor by DIBH. Beacon position stability will be determined on acquired cone-beam CTs by measuring the distance of the beacons to the center of the gross target volume {GTV} as well as the distance of the beacons to each other. Improvement of normal tissue dosimetry based on Calypso-guided DIBH will be determined from the treatment plans developed on the free-breathing and DIBH simulation CT scans. Specific dosimetric parameters will include the chest wall V30, total lung V20, mean lung dose, lung toxicity model metrics (Lyman model NTCP and parallel model fraction damaged (fdam)), mean and maximum esophageal dose, and maximum spinal cord dose.

To determine the minimum clinically feasible gate margins we will decrease the gate in a step-wise progression as far as a minimum of 2 mm. The gate will be reduced from +/- 5mm by 1mm for every 5 patients treated. Halving of the duty cycle will be considered the minimum gate that is clinically feasible. Once the minimum gate is determined, the remaining patients will be treated at +1mm from this value.

In the additional 10 conventionally fractionated patients, tumor shrinkage will be summarized as relative shrinkage in a percentage. Beacon position and centroid are 3D coordinates that will be determined as a distance from a landmark such as a bone or the carina.

Lung volume preservation will be assessed on wide field of view cone-beam CTs and compared intra- and interfraction within each patient to check for reproducibility or variability of lung volumes across multiple DIBH maneuvers.

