
The study will determine for the first time based on real-time tumor positioning information whether patients are able to reproducibly hold their breath in DIBH within excursions of 5.+-0.5cm or less. Furthermore, it will determine whether visual biofeedback improves the reproducibility of the breathhold. It will provide a unique dataset that will allow us to determine the concordance level of real-time tumor position information from the Calypso transponders, external surface signal and radiographic imaging. Ultimately, this study will allow us to quantify the decrease in radiation dose to organs at risk, decreased toxicity and amount of dose escalation made possible by the DIBH maneuver using real-time tumor position information.

Patients will be considered evaluable for protocol when they have had successful calypso beacon implantation without the beacons migrating> 5cm, and they have completed training in DIBH. In the extension of the protocol described below, 25 patients will be accrued; the expected time for completion of this study is 3 year from its approval.

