9.0 TREATMENT/INTERVENTION PLAN

Using ENB and rEBUS, three Calypso transponders will be bronchoscopically placed within a small bronchial airway according to the Anchored Beacon Transponder Instructions for Use provided by Varian Medical (see section 20.0 Appendices). Two Calypso transponders will be permissible if it is technically not possible to place three transponders, as the tracking system works with a minimum of two transponders. Placement within 2 cm from the pleura should be avoided if possible to minimize the risk of pneumothorax. The position of the anchored transponders will be verified by fluoroscopy at the time of placement.

After a minimum of 3 days, the patient will be brought to the radiation simulation suite and immobilized using a custom-mademold, as per our standard protocol. Immobilization will be in a supine position unless prone treatment is required to meet the distance requirement

between the Calypso beacons and the Calypso detector plate. The patient will be coached through the DIBH maneuver and a breath-hold level that the patient can comfortably and reproducibly achieve using the Calypso system will be determined. A free-breathing (FB) 4D CT scan of the thorax and a CT scan in DIBH mode will be obtained using the RPM system. The patient's position and setup will be documented by tattoos and photographs.

Target volumes and normal structures will be delineated on the FB scan and on the DIBH scan. Target delineations will be performed on the registered 4DCT image set and on the DIBH scan as per current clinical practice. The Calypso beacons will also be delineated on each phase of the 4DCT study and on the DIBH scans.

Analysis of the 4DCT will provide an initial evaluation of the motion concordance between the Calypso beacon and the RPM external marker. Two radiation treatment plans will be developed, one based on the free-breathing scan and one based on the DIBH scan. These will be used for dosimetric comparison of treatment plans between a free-breathing and DIBH treatment. Only the DIBH treatment plan will be used clinically, unless a patient is unable to complete the DIBH maneuvers at the time of treatment. In that case, the plan based on the FB scan will serve as a backup plan. The beacon coordinates for the DIBH scan will be input to the Calypso system.

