14.0 BIOSTATISTICS

The primary objective of this nonrandomized study is to test the feasibility of anchored Calypso transponders to guide and monitor DIBH radiation treatments. Feasibility is defined as patients being able to successfully complete the course of treatment. Patients who cannot have their transponders placed accurately bronchoscopically and for whom Calypso-guided DIBH will not be possible as a consequence of that will be considered a failure. Patients who are removed from the protocol as a result of being unable to perform the breath hold for 3 consecutive treatment days at any point in the treatment course for reasons that are not related to the Calypso transponders, Calypso detection or complications of using the Calypso implantation or system (e.g. disease progression, severe side effects from treatment, e.g. esophagitis, infections, failure to thrive, generalized weakness, low blood counts etc.), will be replaced by new evaluable patients. The patients who are removed will be treated with the free-breathing backup radiation treatment plan. The reason for the patient's inability to hold their breath will be recorded.

For this objective the first and second set of 25 evaluable patients will be stratified and analyzed separately. Some details are provided below.

We will enroll 30 patients upfront and we expect that at least 25 evaluable (DIBH training can be done and Calypso beacons can be implanted without migrating > 5cm) patients can be used in

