assessing the feasibility rate. To establish the decision rule we will compute the sample feasibility rate (i.e., the number of patients who could be successfully treated divided by the total number of evaluable patients, which we expect to range from 25 to 30) and form an 80% 2-sided Clopper-Pearson exact confidence interval. If the lower bound of this exact confidence interval is greater than 66% then we will declare this procedure feasible. Namely, we will test the hypotheses $H_0: \theta \leq 0.66$ vs. $H_1: \theta > 0.66$ at $\alpha=0.05$, where θ denotes the feasibility rate. The test statistic will be the lower bound of the 90% 2-sided Clopper-Pearson exact confidence interval for binomial trials. Equivalently, this test statistic can be written as $\text{Beta}(0.05, X, N+1-X)$, i.e., the 5th-percentile of the beta distribution with two parameters X and $N+1-X$, where X and N denote the number of successes and the total sample size (expected to be from 25 to 30), respectively. When the sample size is as small as 25, the power of rejecting the null hypothesis is 61%, 84% and 97% when the true feasibility rate is 0.80, 0.85 and 0.90, respectively. When the sample size is as large as 30, such power becomes 61%, 85% and 97%. Since we expect the feasibility rate to be around 0.85, the sample size is sufficiently large. We expect to finish the recruitment in 4 years.

For protective purposes we will implement a stopping rule to prevent excessive rate of pneumothorax or hospitalization (related to the proposed procedure). If 6 or more events (i.e., procedure-related pneumothorax or hospitalization) among the first 30 patients, or 11 or more events among the total 55 patients we plan to enroll are observed, we will halt the trial to thoroughly investigate such events. This sequential stopping rule has the following probability of halting the trial:

True event probability	0.05	0.08	0.10	0.15	0.20	0.25	0.30
Probability of halting the trial	0.003	0.030	0.081	0.342	0.679	0.900	0.978

In addition, a second stopping rule will be implemented if a maximum of two device migrates to a critical organ, such as the heart or brain, or if one device-related death is observed.

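### Sections 1, 12 and 14 disagree on whether an implanted patient who proves unable to do Calypso-guided DIBH before treatment is a primary-endpoint failure or is left out of the rate

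*Combined protocol and SAP*

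**What the plan says.** **Who is a failure.** Section 12 joins two conditions with 'or': placement that cannot be done accurately, "or for whom Calypso-guided DIBH will not be possible will be considered a failure". The second condition stands alone. Section 14 joins them with 'and' and adds a causal link: "and for whom Calypso-guided DIBH will not be possible as a consequence of that will be considered a failure".

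**Who is evaluable.** Section 1: "Patients will be considered evaluable for protocol when they have had successful calypso beacon implantation without the beacons migrating" more than 5 cm, "and they have completed training in DIBH". Section 14 puts it as ability: "DIBH training can be done and Calypso beacons can be implanted without migrating > 5cm".

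**What is divided by what.** Section 14 defines the primary rate as "the number of patients who could be successfully treated divided by the total number of evaluable patients". It enrols 30 patients at first and expects 25 to 30 of them to be evaluable.

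**When a breath-hold failure can be found.** Section 1 places the transponders first and has the patient learn and practise DIBH afterwards. Section 9 has the patient coached at simulation, at least 3 days after implantation, where "a breath-hold level that the patient can comfortably and reproducibly achieve using the Calypso system will be determined".

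**Replacement.** Sections 12 and 14 replace patients who fail the breath-hold on 3 consecutive treatment days for reasons unrelated to Calypso. That rule concerns treatment days, not the period before treatment.

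**The concern.** Consider a patient whose beacons are well placed and stable but who cannot reach a usable breath-hold before treatment starts. On the literal words of Section 12 this is a failure. Under Sections 1 and 14 the same patient can be non-evaluable because training was not completed or could not be done, and then appears in neither the numerator nor the denominator. Section 14's narrower failure sentence gives no ground for putting the patient back. No section says which text governs.

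This matters because ability to perform the manoeuvre is part of what the study is testing. Section 3.1 says DIBH is currently feasible in about 25% of lung radiotherapy patients because many have difficulty with the manoeuvre, and expects Calypso feedback to make a simpler breath-hold sufficient. A patient who still cannot do it has already had the bronchoscopy. Leaving such patients out conditions the endpoint on part of its own success and moves the rate upward. With 'training' undefined, it also leaves room to settle classification after the outcome is known.

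**Working it through.** **Inputs from Section 14:** null rate 0.66; 30 enrolled, 25 to 30 evaluable; feasibility declared if the Clopper-Pearson lower bound exceeds 0.66. Section 14 names both an 80% two-sided interval (one-sided a = 0.10) and a 90% two-sided interval (a = 0.05), so both are shown. **Assumed, not in the documents:** the share t of implanted patients whose DIBH training fails.

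**Step 1. The plan's own power.** The cut-off is the smallest r for which the a-quantile of Beta(r, N+1−r) exceeds 0.66. Power is P(Bin(N, p) ≥ r).

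| Interval | N | r | Power at 0.80 / 0.85 / 0.90 | P(declare) at 0.66 |
|---|---|---|---|---|
| 80% | 25 | 20 | 61.7 / 83.9 / 96.7% | 0.099 |
| 80% | 30 | 24 | 60.7 / 84.7 / 97.4% | 0.073 |
| 90% | 25 | 21 | 42.1 / 68.2 / 90.2% | 0.040 |
| 90% | 30 | 25 | 42.8 / 71.1 / 92.7% | 0.030 |

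The stated power (61, 84, 97% at N = 25; 61, 85, 97% at N = 30) is reproduced by the 80% interval and not by the 90% interval.

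**Step 2. Level for the evaluable-only rate.** Over N = 25 to 30, P(declare) at a true evaluable rate of 0.66 is at most 0.099 (80% interval) or 0.049 (90% interval). The test is valid for that rate.

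**Step 3. Chance of declaring feasibility when the all-implanted rate is 0.66.** Take 30 implanted patients. The number trained is N ~ Bin(30, 1−t), and all successes lie among the trained, so their success rate is 0.66/(1−t). Then

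P(declare) = Σ over N of P(N) × P(Bin(N, 0.66/(1−t)) ≥ r(N)).

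| t | Rate among trained | 80% interval | 90% interval |
|---|---|---|---|
| 0 (all counted) | 0.660 | 0.073 | 0.030 |
| 5% | 0.66/0.95 = 0.695 | 0.141 | 0.080 |
| 10% | 0.66/0.90 = 0.733 | 0.252 | 0.153 |
| 16.7% (5 of 30) | 0.66/0.833 = 0.792 | 0.498 | 0.325 |

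The last row is an upper limit only. It gives the plan's whole allowance of 5 in 30 to training failure, although that allowance also covers implantation and migration losses.

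**Step 4. Check with a fixed number dropped.** If exactly one of 30 is dropped, the rate among the other 29 is 0.66 × 30/29 = 0.683. P(declare) is then 0.140 (80% interval) or 0.065 (90% interval), each above its nominal 0.10 or 0.05. With three dropped it is 0.235 or 0.117.

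**Step 5. One patient at the cut-off.** Under the 80% interval, 20/25 has lower bound 0.6603 (feasible) and 20/26 has 0.630 (not feasible). Under the 90% interval, 21/25 has 0.670 and 21/26 has 0.637.

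**The case against.** The strongest reply is that the affected group may be nearly empty. Section 6.1 requires five breath-holds of more than 20 seconds, Section 6.2 excludes patients who cannot comply with DIBH instructions, and Section 8 tests the holds with arms raised, usually at consultation. In the earlier spirometry series in Section 3.2, none of seven patients stopped because of inability. 'Completed training' could also mean attendance, in which case a patient who trains poorly is evaluable and counts against the rate. This limits the size of the problem. It does not remove the conflict: Section 14's wording is about whether training can be done, and the clinic screen tests duration before any beacon is in place, not reproducibility on the Calypso signal.

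Second, the documents are not consistent about where such a failure would show. Section 5 lists RPM at the simulator and Calypso at the treatment machine, and Sections 1 and 9 acquire the simulation scans with RPM, yet Section 9 also sets the breath-hold level using Calypso. If Calypso is available only at treatment, some failures first appear when the patient is already evaluable and the three-day rule applies. This objection stands as a reason to reconcile those sections.

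Third, a reader might infer that the test's type I error is inflated outright. The documents do not support that: Step 2 shows that the level holds for the rate Section 14 actually defines. One could also argue that restricting to DIBH-capable patients suits an aim centred on the transponders, in line with the replacement rule. The inflation arises only against the all-implanted rate that Section 12 implies, and no section says that Section 12 controls.

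Finally, a one-patient reversal is a feature of any exact cut-off. Away from the cut-off it does not occur: 21/26 under the 80% interval still passes, at 0.672.

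**Conclusion.** The inconsistency is in the current text and concerns who enters the primary rate. Dropping implanted patients who prove unable to do DIBH makes the reported rate overstate feasibility as Section 12 defines it. If 5% or 10% of 30 implanted patients are lost this way and the true all-implanted rate is 0.66, the chance of declaring feasibility is 14% or 25% under the 80% interval (7% if all are counted), and 8% or 15% under the 90% interval (3% if all are counted).

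These figures rest on assumed shares, because the documents report none, and screening should keep the real share small. The figures of about 50% and 33% at a 17% share should not be read as an expected error rate. The direction of the bias and the need for one rule hold under either interval.

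**What to change.** Use one failure definition and one denominator in Sections 1, 12 and 14:

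- In Section 14, replace the 'and … as a consequence' failure sentence with Section 12's 'or' wording. Without this edit, Section 14 would contradict the new denominator.
- In Sections 1 and 14, remove completed or achievable DIBH training as a condition of being evaluable. State that an implanted patient who cannot reach a usable Calypso-monitored DIBH before treatment counts as a failure in the Section 14 rate.
- Leave the existing replacement rule for non-Calypso reasons during treatment as it is.
- Report the rate among trained patients as a secondary figure.
- Reconcile Sections 1 and 5 (RPM at the simulator, Calypso at the treatment machine) with Section 9 (breath-hold level set using Calypso).
- Settle failed implantation in the same edit. Sections 12 and 14 treat failed placement as a failure, while the evaluable definition removes patients without successful implantation. Correcting that alone would leave the training condition in place.

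The cost is wording. No extra patients or procedures are needed. The reported rate may be slightly less favourable.

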procedures based on external tattoos and room lasers. A free- breathing trace of the Calypso transponders will be obtained to allow the patient to settle on the treatment table and to study real-time respiratory traces. The patient will then be asked to perform a therapist-coached modified slow vital capacity maneuver and DIBH maneuver [1] and hold their breath. Patients will have the ability to perform this maneuver with or without biofeedback from digital goggles that are placed over the patient's eyes and display the breathing trace of the Calypso transponders. The use of the digital goggles will be determined by patient preference or at the discretion of the treatment team. This will allow us to investigate whether real-time biofeedback adds to the reproducibility of patients holding their breath. A DIBH cone-beam CT will be acquired in approximately three breath-holds, once a week for standard fractionated RT patients or with each fraction for SBRT patients. After review and approval of the images, the patient will be treated while holding their breath using the DIBH maneuver. In standard fractionated RT patients the radiation treatment will be guided by the external tattoos and daily 2D kV imaging. The Calypso transponder signal will be used to monitor the level of the breath-hold during treatment. The breath-hold level based on the Calypso transponder signal will be verified daily by the 2D imaging and once a week in 3D by the DIBH cone-beam CT. In SBRT patients, the radiation treatment will be guided by the external tattoos and daily DIBH cone-beam CT. The Calypso transponder signal will be used to monitor the level of the breath-hold during treatment. The therapists will monitor the respiratory trace signal from the Calypso transponders throughout the treatment and will initiate the radiation treatment delivery when the patient holds his/her breath within the tolerance level the patient has been assigned to. This will be continued up until the initially planned 30 patients are accrued.. Should the transponder signal indicate that the target has moved outside of the preset tolerance, the therapists will hold further radiation treatment delivery until the patient's breathhold has returned to the desired target range or until the patient's setup has been corrected. In the additional 25 patients planned, the margins will be reduced in a step-wise fashion. The gate will be decreased 1mm per each set of 5 patients until the duty cycle (beam-on time) and number of DIBH attempts are doubled. The gate at which this occurs will be considered the minimum clinically feasible gate

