In the additional 25 patients to be accrued the window will be reduced in a step-wise fashion by 1mm for every 5 patients. Number of beam holds, treatment interruptions and total treatment time from first beam-on time to the last beam-off time will be recorded by the therapists.

If a patient cannot achieve the desired breath hold after 3 attempts and discussion with the therapist, the therapist can treat with the best breath-hold achievable and report the change in level to the treating physician. Additionally, the therapist will acquire an orthogonal pair of images. The physicist will then estimate the dosimetric effects per day in case the patient is still unable to achieve adequate breath hold the next day. Depending on the estimated dosimetry and the patient's reasons for not being able to achieve breath hold, the patient may be taken off protocol if unable to perform the breath hold to within +/- 5 mm for 3 consecutive treatment days. Patients who are taken off protocol prior to treatment completion will be treated based on the free-breathing treatment planning scan for the remainder of the radiation treatment course.

9.1 For patients undergoing SBRT in 10 or less fractions, the following procedures will be performed:

1. Standard setup procedures based on external tattoos will be performed.
2. The Calypso antenna will be deployed and positioned over the patient's chest. Tracking of the Calypso transponder signal will commence.

3. For patients who have been selected to use the digital goggles, the DIBH maneuver will be performed with visual biofeedback at least once a week and at least one fraction will be done without visual feedback. During treatment the radiation therapist will coach the patient on how to hold their breath during the treatment. On treatment days with visual feedback, the patient will be able to view and control his/her breathing through biofeedback using goggles (Myvu Personal Media Viewer, Myvu Corporation) or an iPhone that displays the Calypso trace. The couch position will be adjusted by the therapists in the treatment room to accurately set up the patient for treatment in DIBH based on the Calypso signal. The Calypso trace will be set to zero based on the DIBH level.
4. The patient will resume regular breathing and the therapists will leave the room.

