For the 1st secondary objective, we will compare the visual vs no visual biofeedback treatments (for patients who agree to use the digital goggles) by the number of treatment interruptions. We expect that there will be fewer treatment interruptions when using biofeedback. To this end Wilcoxon signed-rank tests will be conducted based on the patients who can successfully be treated.

For the 2nd secondary objective, we will assess differences in the ability of maintaining the DIBH maneuver within the fate with and without visual biofeedback. Such differences will be measured as duty cycle, and will be compared using Wilcoxon signed-rank tests based on the patients who can successfully be treated.

For the 3rd secondary objective, the residual intrafraction tumor motion (surrogated by Calypso) will be measured in all 3 dimensions and the euclidean distance will be calculated, which will then be correlated with the normal tissue dosimetry (see end of Section 12.0). Patients will receive multiple fractions and thus multiple measurements of such distance will be obtained from the same patients.

These repeated measures will be averaged for each patient and the correlation will be examined by simple linear regression. If such continuous data are skewed, we may either use an appropriate monotone transformation, or examine the nonparametric correlation coefficient (such as Spearman rank correlation coefficient) between the tumor motion and the normal tissue dosimetry instead.

For the 4th secondary objective, the potential increase in dose escalation and decrease in margins made possible by Calypso- guided DIBH, as contrasted to those obtained from the 40 CT scan, will be formulated as pair data from each patient and tested by using Wilcoxon signed-rank tests. Dosimetric parameters listed at the end of Section 12.0 will be used again for such analysis.

The 5th secondary objective does not require statistical analysis. See Section 12.0 for details.

For the 6th secondary objective, tumor shrinkage, beacon position and centroid changes in conventionally fractionated patients (totally 10), all measured as continuous variables, will be summarized descriptively.

For the 7th secondary objective, intra- and inter-fraction variation in lung volume preservation of multiple DIBH maneuvers will be recorded within each patient and summarized descriptively.

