15.2 Randomization

No randomization will occur in this study.

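### The with/without-goggles comparison has no set order of fractions and no adjustment for time, so a learning or fatigue trend can be confounded with visual biofeedback (secondary objectives 1 and 2)

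*Combined protocol and SAP*

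**What the plan says.** - **Exposure, Section 12.0:** "Each patient will have the goggles 50% of the treatments and without goggles the other 50% of the time". No order is given.
- **Exposure, Sections 9.1 and 9.2, step 3:** for patients selected to use goggles, the maneuver is "performed with visual biofeedback at least once a week and at least one fraction will be done without visual feedback". The wording is the same for SBRT and standard fractionation.
- **Who uses goggles:** Section 1.0 states "The use of the digital goggles will be determined by patient preference or at the discretion of the treatment team". It does not say whether this is decided once per patient or day by day. Section 14.0 makes the first comparison "for patients who agree to use the digital goggles) by the number of treatment interruptions".
- **Allocation, Section 15.2:** "No randomization will occur in this study". No section gives a sequence, alternation or balancing rule for fractions.
- **Expected direction, Section 14.0:** "We expect that there will be fewer treatment interruptions when using biofeedback".
- **Test:** Section 14.0 uses Wilcoxon signed-rank tests for both objectives; duty cycle "will be compared using Wilcoxon signed-rank tests based on the patients who can successfully be treated". Section 12.0 names a rank sum test for duty cycle instead. Neither section includes a term for fraction number or period.

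**The concern.** The comparison is a within-patient crossover in all but name. In a crossover, the order of conditions protects against change over time, and here the order is left open.

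The plan itself makes change over time plausible. Section 8.0 has patients practise at home and be coached again at treatment, so performance may improve. Sections 12.0 and 14.0 expect some patients to lose breath-hold ability through esophagitis, weakness or progression. Those who fail on three consecutive days leave the protocol, but a milder decline in patients who stay on is a reasonable inference.

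The signed-rank test assumes that, with no effect, within-patient differences are symmetric about zero. If goggle fractions fall later on average than the others, any trend moves the center of those differences. The trial could then report a biofeedback benefit, or miss one, for reasons unrelated to the goggles. A missing schedule cannot be restored after treatment.

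**Working it through.** The plan gives no sample size, significance level, effect size or variance for this comparison, so there is no stated figure to reproduce.

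**1. What the exposure rules allow.** Inputs: 30 fractions (Section 3.1, 60 Gy in 30) and SBRT in 10 or fewer fractions (Section 9.1). Five fractions per week is my assumption. Under step 3, the number of goggle fractions runs from the number of weeks up to n − 1.

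| Course | Allowed by step 3 | Even split | Even split meets step 3? |
|---|---|---|---|
| 30 fractions, 6 weeks | 6 to 29 (20% to 97%) | 15 | Yes |
| 10 fractions, 2 weeks | 2 to 9 (20% to 90%) | 5 | Yes |
| 4 fractions, 1 week | 1 to 3 (25% to 75%) | 2 | Yes |
| 5 or 3 fractions, 1 week | 1 to 4, or 1 to 2 | Not a whole number | Exact 50% impossible |
| 1 fraction | None | None | Neither rule can be met |

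Step 3 is therefore looser than Section 12.0 rather than opposed to it. The looseness also costs precision. With equal variance per fraction, the variance of a patient's difference is proportional to 1/15 + 1/15 = 0.133 at 15:15 and to 1/29 + 1/1 = 1.034 at 29:1, which is 7.8 times larger.

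**2. Spurious difference under a linear trend.** Let the mean go from a to b over n fractions, with no goggle effect. The expected with-minus-without difference is (b − a)/(n − 1) × (mean fraction number with goggles − mean fraction number without).

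The latest-loaded 15:15 order that still has one goggle fraction in every week uses fractions 5, 10, 15 and 19 to 30.

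- Mean position with goggles: (5 + 10 + 15 + 294)/15 = 324/15 = 21.6.
- Mean position without: (465 − 324)/15 = 141/15 = 9.4.
- Gap: 12.2 fractions.
- Interruptions falling from 3.0 to 2.0: −1.0 × 12.2/29 = −0.42 per fraction.
- Interruptions falling from 2.5 to 2.0: −0.5 × 12.2/29 = −0.21 per fraction.
- Strict alternation over 30 fractions: the gap is 1, so the shift is 1/29 = 0.034 of the total trend.
- Strict alternation over 4 fractions with a fixed start: the shift is 1/3 = 0.33 of the total trend. Alternating the start between patients cancels it on average.

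Reversing the order, or the trend, reverses the sign.

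**3. False-positive rates by simulation.** Assumptions, none from the documents: no goggle effect; Poisson interruptions with a linear trend; gamma patient effects with shape 4; two-sided 5% signed-rank test on per-patient differences in mean interruptions per fraction.

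| 30 fractions | Fall 3.0 to 2.0 | Fall 2.5 to 2.0 |
|---|---|---|
| Extreme order meeting both rules, 20 patients | about 83% | about 34% |
| Same order, 10 patients | about 47% | about 18% |
| Alternation with alternated start | about 4% to 5% | about 4% to 5% |

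At 4 fractions (fall 3.0 to 2.0, 20 patients), alternation with a fixed start gave about 17% and with an alternated start about 4%. Repeat runs move these rates by a few percentage points.

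**4. If goggles were chosen on harder days.** Assume day difficulty is 25% of the variance and the log-odds of goggle use rise by 0.5 to 1 per SD of difficulty. The spurious difference at 30 fractions is then +0.23 to +0.41 SD, against goggles.

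**The case against.** The strongest reply is that this is a non-randomized feasibility study. Section 4.1 presents the secondary objectives as exploratory, and the goggles comparison has no decision rule. The inputs above are assumed: the plan gives no interruption rate, trend or number of goggle users, and goggles are optional. Learning and fatigue could partly cancel. The order in step 2 is adversarial, and no section asks for it. All of this stands. It limits the weight of the point, but it does not supply a missing order.

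Three stronger readings are tempting, and the documents do not support them.

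- **The two exposure rules contradict each other.** They do not. Step 3 says at least weekly with goggles and at least one fraction without, and an even split meets both in most even-numbered courses. The firmer tension is between a fixed 50% for each patient in Section 12.0 and optional use in Sections 1.0 and 14.0.
- **All goggle fractions could fall in the second half of a 30-fraction course.** In the same simulation with 20 patients this gives 95% and 48% false positives. However, it leaves weeks 1 to 3 without goggles and breaches step 3, so those rates do not describe a compliant schedule.
- **Goggles used on difficult days would pass for a benefit.** Section 1.0 permits day-by-day choice but does not state it, and the references to patients who agree or are selected suggest a choice made per patient. If it did happen, goggles would look worse, which would hide or reverse the expected benefit.

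**Conclusion.** The point holds. The comparison behind secondary objectives 1 and 2 has no schedule of conditions, its exposure wording allows anything from about 20% to 97% goggle fractions on a 30-fraction course, and its tests take no account of time. A trend can therefore be mistaken for a biofeedback effect or can mask one.

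The size depends on assumed trends and on the order actually used. The percentages show what a compliant but unlucky schedule could do. They do not forecast the trial's error rate.

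A reader might infer that the trial's main conclusion is at risk. It is not: the feasibility endpoint, its sample size and the stopping rules do not use this comparison. Severity is moderate, and the label is cheap improvement.

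**What to change.** 1. Replace step 3 in Sections 9.1 and 9.2 with one rule consistent with Section 12.0. For patients who agree to goggles, alternate fractions with and without visual feedback, as near to half as the course length allows.
2. Alternate or randomize the starting condition between patients. Short SBRT courses need this, because a fixed start leaves bias. If the start is randomized, amend Section 15.2 to say so.
3. State in Section 1.0 that preference or team discretion decides whether a patient takes part in the goggles comparison. Record any later departure from the schedule with its reason.
4. Analyze by scheduled condition, and leave single-fraction courses out of objectives 1 and 2.
5. Name the paired signed-rank test for duty cycle in both Section 12.0 (now rank sum) and Section 14.0.
6. For any patients already treated under the present wording, report which fraction numbers fell in each condition.

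The cost is a wording amendment and a pre-filled fraction list for the therapists, with no extra patients, visits or equipment. The small downside is less freedom over which days use goggles.
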